#### **4.2.5. Reasons for withdrawal**

After enrollment, a participant might be withdrawn from participation for several reasons:

- The investigator requests withdrawal because the participant:
  - Is not eligible or is no longer eligible;
  - Developed an AE or SAE requiring withdrawal; or
  - Is non-compliant.
- A participant voluntarily withdraws at his/her own request;
- A participant is lost to follow-up; or
- The trial is terminated prematurely by PATH.

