#### **4.2.7. Termination of the trial**

The trial might be suspended at any time by PATH or by any ethical review committee overseeing this study for any safety concern. This includes, for example, and without limitation, an SAE resulting in death that is viewed to be related to receipt of study vaccine or an unusually high rate of SAEs. PATH may suspend the study in the event that study conduct is found to be below Good Clinical Practice (GCP) standards.

In the event of the appearance of new data that indicate an increased level of risk to participants, the clinical trial will be suspended until PATH and all ethical review committees have reviewed relevant data and agreed that the trial may proceed.

Withdrawal of a participant by the investigator may occur only if the participant is identified to have one of the listed exclusion criteria, or if continued participation of the participant threatens the participant's well-being or the integrity of the study. Any participant with an adverse event related to involvement in the trial should continue to be followed for safety reasons until trial conclusion or resolution of the adverse event.

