#### 7.8.5. Allowable schedule of study visits

For clarity, per-protocol timing of key study visits is provided below in Table 4. No child should be dropped from the study solely on the basis of a visit falling outside of an allowable time-frame for that visit if there is good faith attempt by study staff and the child participant's parent(s)/guardian(s) to adhere to the protocol.

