3.1.1. Intention-to-Treat Analysis Set

For immunogenicity analysis on long-term assessment of the anti-JE antibody response to CD-JEV, the ITT analysis set will include all enrolled participants in this study whether the participants receive a booster dose of CD-JEV or not. The participants who have at least one serology result in Year 3 (Visit 01) or Year 4 (Visit 02) prior to the booster dose will be included in the long-term assessment.

For the immunogenicity analysis on antibody response following a booster dose of CD-JEV, the ITT analysis set will include those participants who receive the booster dose and have at least one serology result on 7 days (Visit 09) or 28 days (Visit 10) post booster vaccination.

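### Protocol 4.2.5 and 4.2.7 give different grounds for investigator withdrawal, and neither separates withholding the single booster from ending data collection after it

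*Protocol*

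**What the plan says.** Protocol 4.2.5 opens with "After enrollment, a participant might be withdrawn from participation for several reasons" and sets no time limit. The investigator's grounds are that the child is not or no longer eligible, "Developed an AE or SAE requiring withdrawal; or", and "Is non-compliant". The protocol does not define what makes an event require withdrawal, or what counts as non-compliance.

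Protocol 4.2.7, under a heading about terminating the trial, is restrictive: "Withdrawal of a participant by the investigator may occur only if the participant is identified to have one of the listed exclusion criteria". The one alternative it admits is a danger to the child's well-being or to study integrity. Its next sentence adds: "Any participant with an adverse event related to involvement in the trial should continue to be followed for safety reasons", until the trial ends or the event resolves.

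Protocol 7.8.5 says "No child should be dropped from the study solely on the basis of a visit falling outside of an allowable time-frame for that visit", on condition that staff and parents tried in good faith to keep to the schedule.

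Protocol 4.2.6 asks, on premature withdrawal, for a best-effort interview about reactions in the three weeks after vaccination and a completed final-visit form. The adverse event and SAE endpoints run to 28 days (Protocol 2.4 and 6.2; SAP 7.1).

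One booster is given, at Visit 02. Home visits on Days 1 to 6 and clinic visits with blood draws on Days 7 and 28 follow (Protocol section 4 and Table 3). SAP 3.1.1 limits the booster ITT set to "those participants who receive the booster dose and have at least one serology result on 7 days (Visit 09) or 28 days" after it. SAP 3.3.1 imputes no missing serology and analyses it as randomly missing. SAP 3.1.3 keeps every boosted child in the safety set.

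**The concern.** Two sites, or two investigators, could apply different sections to the same child, most obviously to a non-compliant one. The second difficulty is timing. Withdrawing a child before Visit 02 prevents a dose. Withdrawing the same child afterwards prevents no dose, but ends the remaining blood draws and the scheduled adverse event inquiry. The protocol uses one word for both.

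What is at stake is selective loss in the secondary objectives. A post-booster exit for an adverse event or for non-compliance is not a random event. The SAP nevertheless treats the missing titre as random, and a set labelled ITT omits the child because of something that happened after the dose. On the safety side the child still counts in the denominator, while later events may go unrecorded.

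**Working it through.** **1. Grounds compared.**

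| Ground | 4.2.5 | 4.2.7 |
|---|---|---|
| Ineligible | Named | Named, as a listed exclusion criterion |
| AE or SAE | Named, threshold undefined | Not named; can fall under well-being |
| Non-compliance | Named, unqualified | Not named; only some cases fit study integrity |

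The restrictive wording of 4.2.7 makes the non-compliance row a real difference. Section 7.8.5 narrows what non-compliance can mean; it is not a third set of grounds.

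**2. What a withdrawal removes.** Section 4.2.6 requests a form but names no blood sample, so I assume none is taken at exit.

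| Time of withdrawal | Day 7 / Day 28 titre | Booster ITT set | Booster PP set | Safety set |
|---|---|---|---|---|
| Before the booster | none / none | out | out | out |
| After the booster, before Visit 09 | missing / missing | out | out | in |
| After the Visit 09 sample, before Visit 10 | present / missing | in | out | in |

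The second row is the problem case for the ITT set. In the third row the child stays in the set, but the Day 28 titre is missing.

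**3. What is still followed.** Section 4.2.7 keeps related adverse events under follow-up, and 7.2.3 follows reported reactogenicity until it resolves or stabilizes. Neither secures the two sera, new events, events judged unrelated, or any follow-up of a child withdrawn for non-compliance. The 4.2.6 interview covers 21 days against a 28-day window, which leaves 28 − 21 = 7 days outside it.

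**4. Size.** SAP Table 2 is the only planning figure. Its widths are full Wilson widths, 2z/(1 + z²/n) × √(p(1−p)/n + z²/(4n²)), with z = 1.96 and n rounded down. For Group B at 80% seroprotection and 20% attrition, 163 × 0.8 = 130.4, so n = 130:

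- 2 × 1.96/1.02955 × √(0.0012308 + 0.0000568) = 0.1366, printed as 0.137.

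All 40 cells reproduce to three decimals. That attrition is non-enrolment; it is not withdrawal after the booster, for which no rate is given.

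The following rests on assumptions: 20% non-enrolment, Day 28 seroprotection of 95%, and a share w of boosted children with no Day 28 result.

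- *Precision.* From w = 0 to w = 10%, the width goes from 0.0378 (n = 524) to 0.0398 (n = 472) in Group A, and from 0.0782 (n = 130) to 0.0828 (n = 117) in Group B. The loss is small.
- *Selective loss.* With 95% observed, the rate among all boosted children lies between 0.95(1 − w), if every lost child lacks protection, and 0.95(1 − w) + w, if every one has it. This gives 94.05% to 95.05% at w = 1%, 93.1% to 95.1% at 2%, and 90.25% to 95.25% at 5%.
- *Unsolicited events.* Let w now be the share withdrawn, and q the fraction of those children whose first unsolicited event comes later and goes unrecorded. The 28-day proportion is then too low by w × q, which is at most w. At w = 2% and q = 50%, that is 1 percentage point.
- *Scale in Group B.* 163 × 0.6 = 97.8 and 163 × 0.9 = 146.7 children, so three withdrawals are 3.1% or 2.0%. These bases are enrolled children, so they are ceilings on the number boosted.

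**The case against.** The strongest reply is that the sections can be obeyed together. Section 4.2.5 is permissive, 4.2.7 restricts it, and 7.8.5 bars one ground. A site that withdraws only when 4.2.7 is met, and never solely for a late visit, breaches none of them. The last exclusion criterion in 4.2.4 also mentions compliance with study procedures, so non-compliance can be argued into 4.2.7. This disposes of the inference that a site cannot follow all three. It does not remove the ambiguity: the 4.2.4 criterion is set for the time of vaccination, and reading it onto a boosted child is an inference that sites may or may not make.

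A reader might also infer that a child withdrawn for a reaction on Day 2 is lost to the safety results. The documents do not support that. SAP 7.2 counts children with at least one occurrence, so the reaction is already counted, and 4.2.7 and 7.2.3 keep it under follow-up. Any undercount concerns later unsolicited events.

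Nor is it right that only observation is lost. Two venipunctures remain after the booster, Protocol 3.5.1 lists venipuncture as a risk, and an investigator may have reason to stop them.

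Finally, SAP 4.2 tabulates discontinuations with reasons, and valid serology by visit and group. Loss would therefore be visible, though the tables cannot recover it.

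**Conclusion.** The point holds as a minor one. The two withdrawal sections differ, most clearly on non-compliance, and neither says whether a child who has had the booster should still give sera and be asked about adverse events. The permitted loss can be related to outcome, while the SAP treats missing titres as random and keeps the child in the safety denominator.

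The effect is probably small. It depends on a post-booster withdrawal rate that the documents do not give, so the figures above are bounds under assumed rates and not forecasts. A reader might infer that the main persistence results are at risk. They are not, because the Year 3 and Year 4 samples are taken before the booster, and no post-booster withdrawal can alter them. The three-week interview against the 28-day event window is a separate, plain mismatch.

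**What to change.** Reconcile Protocol 4.2.5, 4.2.6, 4.2.7 and 7.8.5 into one rule that the other sections cite, and have it distinguish booster not given from data collection ended. Which clinical grounds justify withdrawal is for the sponsor to settle. The well-being ground in 4.2.7 should stay.

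For data collection, state that once the booster has been given, non-compliance or later ineligibility does not by itself end it. Adverse event and SAE inquiry continues to Day 28, and the Day 7 and Day 28 samples are still sought, subject to parental consent and the investigator's well-being judgement. Align the 4.2.6 interview with the 28-day window. Handle deviations through the PP set in SAP 3.1.2, which already exists for that purpose.

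The cost is one wording amendment. The downside is that a few more children with deviations remain in the ITT set; the PP analysis shows the results without them.

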#### **4.2.6. Handling of withdrawals**

In case of premature withdrawal for any reason, the investigator should use his/her best effort to:

- Conduct an interview to determine if the participant has had any reaction or AE (serious or non-serious) that has led to the withdrawal during the three-week period after any study vaccination. Where possible, the investigator should visibly or physically assess any reported adverse reaction or AE.
- Document the reason for premature withdrawal on the case report form (CRF).
- Complete final visit CRF.

The investigator must inform PATH within 7 days of becoming aware about of the premature termination of a volunteer's participation in the trial.

#### **4.2.7. Termination of the trial**

The trial might be suspended at any time by PATH or by any ethical review committee overseeing this study for any safety concern. This includes, for example, and without limitation, an SAE resulting in death that is viewed to be related to receipt of study vaccine or an unusually high rate of SAEs. PATH may suspend the study in the event that study conduct is found to be below Good Clinical Practice (GCP) standards.

In the event of the appearance of new data that indicate an increased level of risk to participants, the clinical trial will be suspended until PATH and all ethical review committees have reviewed relevant data and agreed that the trial may proceed.

Withdrawal of a participant by the investigator may occur only if the participant is identified to have one of the listed exclusion criteria, or if continued participation of the participant threatens the participant's well-being or the integrity of the study. Any participant with an adverse event related to involvement in the trial should continue to be followed for safety reasons until trial conclusion or resolution of the adverse event.

### **4.3. Study vaccine**

#### **4.3.1. Live, attenuated JE vaccine SA 14-14-2**

SA 14-14-2, the vaccine virus strain, was attenuated by an empirical process of serial passage of the wild-type SA 14 virus in cell cultures of primary hamster kidney (PHK) cells and in animals (mice, hamsters) with successive plaque purifications (in primary chick embryo cells). SA 14-14-2 virus has 57 nucleotide changes compared to the parent SA 14 virus, resulting in 24 amino acid changes. Genetically-stable mutations resulting in 8 amino acid changes in the E protein gene are associated with reduced neurovirulence (attenuation).

CD-JEV is a preparation of SA 14-14-2 grown in culture on a monolayer of PHK cells. After cultivation and harvest, an appropriate stabilizer is added to the virus suspension, which is then lyophilized. Live attenuated JE virus (strain SA 14-14-2), minimum essential medium, and human serum albumin are the major components of the final vaccine.

The vaccine is prequalified by the WHO and produced in accordance with technical specifications in "Guidelines for the production and control of Japanese encephalitis vaccine (live) for human use" developed by the WHO Expert Committee on Biological Standardization, Chinese Pharmacopoeia and registered standard of Chinese State Food and Drug Administration (No.WS4-(ZB-072)-2010).

#### **4.3.2. Acquisition**

The investigators or designee will be personally responsible for receiving the vaccine within Bangladesh and all subsequent management of study vaccines. Appropriate vaccine acquisition and handling standard operating procedures (SOPs) will be developed in collaboration with the investigator. Extra doses of vaccines will be provided and shall be used when the initially allocated dose is broken, damaged, or unusable.

PATH will coordinate direct shipment of CD-JEV from CDIBP to a central location in Bangladesh. The manufacturer, CDBIP, will donate these vaccines free of charge. The investigator or designee will receive the vaccine, provide customs clearance, and deliver the vaccine to a central facility under controlled cold-chain conditions. The investigators and their institution will receive no monetary compensation from the manufacturer for their participation in this study.

#### **4.3.3. Packaging and labeling**

The study vaccines will be provided in their commercial presentation. The commercial vial labels for these vaccines should remain intact. An additional label will be affixed by the manufacturer to each box and will bear the following information:

- Study number
- Legal information: “For Clinical Trial Use Only”

#### **4.3.4. Product storage and stability**

CD-JEV vaccine should be stored in a refrigerator or cold box at a temperature ranging from +2°C to +8°C and protected from light. Storage temperature should be monitored and documented on an appropriate form during the entire trial.

The vaccines should never be frozen. In case of deep freezing or accidental disruption of the cold chain, the vaccine should not be administered and the investigator or the responsible person should contact the study monitor to receive further instructions.

#### **4.3.5. Dosage, preparation and administration of study vaccines**

CD-JEV will be supplied in 5-dose vials as a lyophilized powder that looks like a milky-white crisp cake. After reconstitution, it turns into a transparent orange-red liquid. Each 0.5 ml human dose for subcutaneous injection contains no less than 5.4 log PFU of live JE virus. A single dose of 0.5mL should be administered by subcutaneous injection with the rest of the vial discarded.

The vaccines should be gently shaken prior to administration to assure homogenous suspension. CD-JEV will be administered subcutaneously into the anterolateral aspect of the right upper arm.

Standard immunization practices should be observed and care should be taken to administer the injection. As with all injectable vaccines, appropriate medical treatment, staff, and supervision will be readily available in case of rare anaphylactic reactions following administration of the study vaccine and epinephrine 1:1000, diphenhydramine, and resuscitation equipment should be available in case of any anaphylactic reactions.

#### **4.3.6. Accountability procedures**

Study vaccine must be kept in a secure place. The investigator or the person in charge of vaccine management will maintain records of the vaccine's delivery to the trial site, the inventory at the site, the dose given to each participant, and the return or disposal of unused doses to PATH. Appropriate vaccine accountability SOPs will be developed in collaboration with the investigator.

### **4.4. Study procedures**

#### **4.4.1. Recruitment and screening information**

Participants of JEV05 will be identified from the computerized HDSS database and dataset from the previous study maintained at the field site in Matlab and Mirpur. Field workers will visit their homes and explain to the parent or legal guardian the study purpose and procedures. If the parent or legal guardian is interested in having

their child participate in the study, field staff will invite them to come to their nearby FSC on a scheduled enrollment day.

All participants from JEV05 that continue to live in the study area are eligible to participate in this study. We propose to include children that were seronegative at 28 days because there is an indication from other studies that participants seronegative at D28 may generate a detectable antibody response at a later timepoint. Furthermore, we expect that some “seronegative” participants, can generate an anamnestic response. The serum collected at Day 7 following the booster dose will be used to determine whether previously vaccinated children who did not have any antibody at 3 and 4 years post CD-JEV vaccination can generate an anamnestic response (i.e., the children were immune to JE disease). Although serum neutralizing antibody is generally considered our best correlate of protection, there are instances where vaccinated persons without antibody level are nevertheless truly immune and they are able to mount a complete and normal immune response should they become infected. The way to determine this is to look at the anamnestic immune response, i.e., short-term antibody response. This is an antibody response that is not due to a new primary response; it depends on having primed B and T lymphocytes ready to respond quickly. The magnitude of the response measured between Day 7 and Day 28 will indicate whether the participant is mounting an anamnestic response to the booster or a primary response.

#### **4.4.2. Enrollment (Visit 01, 3 years after JEV05 vaccination $\pm$ 3 months)**

When the parent or legal guardian brings their child to the FSCs on the scheduled day for enrollment, the study team will:

- Describe the study to the parents, including the study purpose, requirements, duration, and risks and benefits of the study. The parent or legal guardian will have the opportunity to ask any questions.
- Assess the family’s ability to comply with study requirements.
- Obtain written informed consent. Participation in the study is strictly voluntary, and those agreeing to participate must provide a written informed consent. The consent form will be in Bangla. The parent(s) or guardian(s) will be informed that they are free to refuse to have their child participate and also to withdraw their consent at any time. One parent’s or guardian’s signature is acceptable as informed consent for this study. If the parent or guardian is illiterate, a left thumb impression will be taken instead of signature in the presence of an impartial literate witness who is unrelated to the study. The impartial literate witness (hierarchically independent of the PI and not specified on the list of trial contributors) will also sign the informed consent form and attest that the information in the consent form and any other written information were explained to the parents or guardian and that the information was understood. Following the informed consent process, the child will be enrolled into the study.
- Collect demographic and address information.
- Collect pertinent medical history through parent interview, including data on child’s health and previous vaccinations and reaction to vaccinations and history of any chronic or recurrent medical conditions.
- Perform a physical exam (temperature, height and weight, a brief examination of the head, neck, heart, lungs, abdominal region, musculoskeletal system, and skin).
- Review study inclusion and exclusion criteria and determine eligibility.
- Assign the child a unique study participant number following confirmation of eligibility and consent.
- Collect 2 ml of blood with aseptic technique to detect anti-JE serum neutralizing antibody with the PRNT-50.
- Participants will be reminded that study staff will be contacting them in approximately one year for administration of a booster dose of CD-JEV.

#### 4.4.3. Vaccine administration (Visit 02, 1 year after Visit 01 $\pm$ 28 days)

When the parent or legal guardian brings their child to the FSCs on the scheduled day for vaccination, the study team will:

- Describe the study to the parents, including the study purpose, requirements, duration, and risks and benefits of the study. The parent or legal guardian will have the opportunity to ask any questions.
- Reassess the family's ability to comply with study requirements.
- Collect demographic and address information.
- Collect pertinent medical history through parent interview, including data on previous vaccinations and reaction to vaccinations and history of any chronic or recurrent medical and psychiatric conditions.
- Perform a physical exam (temperature, height and weight, a brief examination of the head, eyes, ears, nose, throat, neck, heart, lungs, abdominal region, lymph nodes, musculoskeletal system, and skin).
- Review exclusion criteria and determine eligibility for blood draw and booster vaccination.
- Collect 2 ml of blood from participants with aseptic technique to detect anti-JE serum neutralizing antibody and anti-JE IgM with PRNT-50 and ELISA, respectively.
- Administer CD-JEV vaccine subcutaneously in the anterolateral aspect of the right upper arm according to standard sterile techniques.
- Ask the parents to wait with the child in the clinic for 30 minutes after the vaccination(s) to assess immediate reactions. If the child experiences an adverse reaction or a SAE during this time period, he/she will be treated and the event will be recorded on the CRF.
- Inform the parents that they will be visited daily for the next 6 days in order to check on the welfare of the child and assess the occurrence of any local or systemic reactions.
- Remind the parents to seek medical care as appropriate and inform the investigator as soon as possible in the event of an adverse reaction or SAE. If the child visits a health care provider, the parents should be sure to inform him/her of the child's participation in the study and present the provider with contact information for the investigator as indicated on the study identification card.
- Give the parents a study identification card that indicates that the child has been enrolled in a research study and given a study vaccine. The card will contain the following information:
  - Name, address, and contact phone numbers of local PI.
  - Vaccination clinic location.
  - Name of vaccine given to child.
  - Schedule of visits.
  - Indication that the child is in a vaccine trial and a request that medical personnel who treat the child contact the local PI within the study duration.
- The appropriate section(s) of the CRF will be completed.

